2.7 Adjustment for non-standardized test conditions

If a test distance other than 4 meters is used for refraction and in a location other than the certified visual acuity lane (Section 1.5), a final refinement of the spherical power (as outlined in Section 2.6, Refining final spherical power) should be performed in the certified lane at 4 meters just before visual acuity testing, using Refraction Chart R with appropriate lighting. If the refinement power differs from the initial refraction, this lens correction should be recorded on the Visual Acuity Worksheet. Similarly, if a phoropter is used for the subjective refraction, a final check of the spherical power (as described in Section 2.6) should be performed with a trial frame using the 4 meter refraction lane and Refraction Chart R. A change of spherical power in these circumstances only requires rechecking the cylinder power if the sphere changes by 0.50 diopters or more.

2.8 Refraction for participant with poor visual acuity

If it is not possible to perform refraction at the 4 meter distance because of decreased vision or impaired mental aptitude, which prohibits the participant from correctly reading 4 or more letters, the refraction should be attempted at 1 meter. Before attempting the 1 meter refraction, +0.75 sphere must be added to the last 4 meter refraction obtained (during follow-up this is the previous refraction result obtained from the refraction data sheet), which is to be used as the starting refracting. If the subjective refraction can be successfully performed at 1 meter, a +0.75 sphere should be subtracted from the final 1 meter refraction to make the correction appropriate for the 4 meter distance. The refraction procedure at 1 meter is the same as the procedure for 4 meters. However, if the participant is unable to discern changes in letter clarity using the lens increments outlined for the 4 meter refraction, larger increments of lens power should be used. When checking the sphere, \pm 1.00 diopter should be tested. If the participant still cannot perceive any difference in clarity, changes up to \pm 3.00 diopters can be attempted. Cylindrical refraction can be assessed with the 0.50 or 1.00 diopter Jackson cross cylinder rather than the 0.25 diopter cross cylinder. When changing the sphere power, use 1.00 diopter increments for adding plus, and 0.50 diopter increments for adding minus. When changing cylinder power, add or subtract cylinder power in 0.50 diopter increments.

If at the end of the refraction process at 1 meter (still on Chart R), the participant is consistently reading letters on the seventh line or lower, he or she should be moved back to 4 meters, and the procedures for the 4 meter refraction should be followed (still using Chart R).

As always, when testing final visual acuity the testing is started at 4 meters (using Charts 1 and 2).

If it is not possible to perform a subjective refraction at the 4 meter distance because visual acuity is too poor for the participant to see the largest letters on the refraction chart at this distance, the refraction should be attempted at 1 meter. If the subjective refraction can be performed successfully at 1 meter, a \pm 0.75 sphere should be subtracted from the 1 meter refraction to make the correction appropriate for the 4 meter distance. This correction should be entered on the Refraction Worksheet in the space provided for distance subjective refraction. (NOTE: Visual acuity will be tested first at the 4 meter distance even if the participant cannot be refracted at this distance.) If the number of letters read correctly at 4 meters is 19 or less, visual acuity must also be tested at 1 meter, in which case the \pm 0.75 sphere should be added to the 4 meter refraction.

2.9 Special situations

Occasionally, one will need to perform refraction and visual acuity on participants with medical or other conditions that make the routine testing difficult, such as Alzheimer's disease or other problems that make strict adherence to the protocol difficult. In such cases one should attempt to follow the protocol as carefully as possible recognizing the special needs of the participant. For example, some participants are unable to concentrate long several lines. It may be necessary to point to letters to get the participant started at the appropriate line or to get them to read letters at all. The goal is to follow the protocol as closely as possible, recognizing that, on occasion, special circumstances may require some minor deviations to get the best estimate of the participant's true best corrected visual acuity.

3. Testing Best Corrected Visual Acuity

3.1 4 meter test

TESTING OF ALL EYES BEGINS AT 4 METERS. First, the right eye is tested with Chart 1, and then the left eye is tested with Chart 2. Each chart should remain hidden from view until the eye in question is ready for testing.

The distance from the participant's eye to the visual acuity chart must be exactly 4.0 meters (13 feet and 1.5 inches, or 157.5 inches). The participant may stand or sit for the 4 meter visual acuity test. If the participant is seated, his or her back should fit firmly touching the back of the chair. The examiner should ensure that the participant is standing or sitting comfortably, that the head does not move forward or backward during the test, and that the participant's eyes remain at the 4 meter distance.

The testing procedure for visual acuity is based on the principle that the objective is to test visual acuity and not intelligence or the ability to concentrate or follow or remember instructions (although all of the factors are involved). The participant should be told that the chart has letters only and no numbers. If the participant forgets this instruction and reads a number, he or she should be reminded that the chart contains no numbers, and the examiner should request a letter in lieu of the number.

The participant should be asked to read slowly (at a rate not faster than about one letter per second) in order to achieve the best identification of each letter and to not proceed until the participant has given a definite response. It may be useful for the examiner to demonstrate the letter-a-second pace by reciting "A, B, C, . . ." If, at any point, the participant reads quickly, he or she should be asked to stop and read slowly. If the participant loses his or her place in reading or the examiner loses his or her place (possibly because the letter are read to quickly), the examiner should ask the participant to go back to where the place was lost. Examiners should never point to the chart or to specific letters on the chart or read any of the letters during the test except for those situations as outlined in Section 2.7.

Each letter is scored as right or wrong (Section 3.3). Once a participant has identified a letter with a definite single-letter response and has read the next letter, a correction of the previous letter cannot be accepted. If the participant changes a response aloud (e.g., "That was a "C", not an "O")

before he or she has read aloud the next letter, then the change should be accepted. If the participant changes a response after beginning to read the next letter, the changes is not accepted.

When the participant says he or she cannot read a letter, he or she should be encouraged to guess. If the participant identifies a letter as one of two or more letters, he or she should be asked to choose one letter and, if necessary, to guess even if the next letter has already been read. The examiner may suggest that the participant turn or shake his or her head in any manner if this improves visual acuity. If the participant does this, care must be taken to insure that the fellow eye remains covered. When it becomes evident that no further meaningful readings can be made, despite urgings to read or guess, the examiner should stop the test for that eye.

There are several reasons for encouraging participants to guess: (1) participants' statements that they cannot identify a letter are often unreliable; (2) encouraging them to guess helps to maximize the participant's effort; (3) it helps to assure uniformity among procedures performed in different clinical centers; and (4) it may help to prevent participant bias (malingering).

3.2 1 meter test

Eyes reading 19 or fewer letters correctly at 4 meters should be tested at 1 meter. If the trial frame is to be removed when changing the test distance from 4 meters to 1 meter, the testing chart (Chart 1 or 2) should first be removed from view to prevent the participant from reading the chart with the fellow eye.

Before testing at 1 meter, a +0.75 sphere should be added to the 4 meter correction already in the trial frame to compensate for the closer testing distance. The participant may stand or sit for the 4 meter test, but must sit for the 1 meter test. (As indicated in Sections 1.5 and 3.1, the participant should be seated comfortably with his or her back firmly placed against the back of the chair.) The avoidance of any head movement forward or backward is particularly important during the 1 meter test. The participant should be asked to read only the first six lines at 1 meter, making 30 the maximum score attainable at that distance (Section 3.3).

After the test of the right eye is completed, occlude the right eye and replace Chart 1 with Chart 2. The test is repeated for the left eye, if indicated by the number of letters read when that eye was tested at 4 meters. When testing of the left eye is completed, Chart 2 should be removed from view. Chart R may be mounted in preparation for the next participant.

3.3 Scoring best corrected visual acuity

The examiner records each letter identified correctly by circling the corresponding letter on the Visual Acuity Worksheet. Letters read incorrectly and letters for which no guesses are made are not marked on the form. Each letter read correctly is scored as one point. The score for each line (which is zero if no letters are read correctly) and the total score for each eye are recorded on the Visual Acuity Worksheet after testing is completed. If testing at 1 meter is not required, 30 points are automatically scored for the 1 meter test. The total combined score (i.e., the sum of the 4 and 1 meter scores) and the approximate Snellen fraction, which is determined based on the lowest line read with one or fewer mistakes, are recorded on the Visual Acuity Worksheet Form.

3.4 Counting fingers, hand motion, light perception, and no light perception

If the participant reads 3 or fewer letters on the 20/800 line at 1 meter, visual acuity is assessed by counting fingers. During this test the examiner holds his or her fingers before the participant's eye good light and the vision is recorded as the furthest distance at which the fingers can be counted. For example, if the participant can accurately count the number of fingers the examiner is holding up from 1 meter (approximately 3 feet) away, this is recorded at counting fingers at 1 meter (approximately 3 feet) on the Visual Acuity Worksheet Form. If the participant cannot distinguish fingers, the examiner should wave a hand in front of the participant's eye. If movements of the hand are perceived by the participants, then the vision is recorded as HM or hand movements.

If visual acuity is so poor that the participant is unable to count fingers or perceive hand motion, light perception should be tested with the indirect ophthalmoscope as the light source. Room lighting should remain at the level of normal visual acuity testing. The subject should close the opposite eye and occlude it by making a tight seal with the palm around the orbit and the bridge of the nose. The indirect ophthalmoscope light should be in focus at 3 feet (approximately 1 meter), the beam should be directed in and out of the eye at least 4 times, and the participant should be asked to respond when he or she sees the light. If the examiner is convinced that the participant perceives the light, vision should be recorded as "light perception"; if not, vision should be recorded as "no light perception."

4. Staff Certification

4.1 Introduction

This section describes the ophthalmic study activities which require certification and the procedures for obtaining and maintaining certification.

It is expected that all ophthalmologists and study personnel will read and become familiar with all aspects of this manual. Study ophthalmologists and Principal Investigators should carefully consider the qualifications of clinical center personnel proposed for certification for the RRR study. Candidates should have experience with basic refraction techniques and the following optical fundamentals:

- Spherical Equivalency
- Plus and Minus Spheres and Cylinders
- Hyperopia, Myopia, and Astigmatism
- "Push Plus" Refraction Principles

4.2 Activities Requiring Certification

Training and certification are required for the following activities:

- ETDRS Refraction
- ETDRS Visual Acuity

In the RRR study, all staff must be fully certified in all study tasks. Full certification in the activities named above must be obtained PRIOR to clinical center staff performing these activities on study participants.

4.3 Forms of Valid Certification

Proof of valid certification (Copy) from Vision Certifying Agency (i.e., Touchstone, EMMES, etc.)

4.4 Study Facilities

The Study Coordinator or other clinical center staff is expected to set up the refraction and visual acuity measurement lane per protocol requirements. If there is a change in the condition or location of the certified examination lane during the course of the study or the office is planning to move, the Study Coordinator is responsible for notifying the sponsor

1. DESCRIPTION OF STUDY

RRR is a phase II, randomized, multicenter, clinical study to assess the tolerability and efficacy of ranibizumab treatment administered in subjects with radiation retinopathy. Subjects will be randomized into one of 3 arms; ranibizumab treatment administered IVT monthly vs. ranibizumab treatment administered IVT monthly combined with peripheral targeted photocoagulation vs. ranibizumab treatment administered IVT for three months followed by as needed treatment of ranibizumab combined with peripheral targeted photocoagulation over 48 weeks. From week 52 to week 1010, all 3 treatment arms will employ a treat and extend protocol for IVT ranibizumab treatment.

2. OVERVIEW OF STUDY DESIGN

This trial will compare the results of 3 different combinations of therapy to assess the efficacy of peripheral targeted retinal photocoagulation (TRP) applied to areas of retinal nonperfusion and poor perfusion combined with ranibizumab injections for the treatment of macular edema secondary to radiation retinopathy. Specifically, this trial will evaluate the ability to reduce the monthly treatment burden by eliminating areas of peripheral ischemia as detected by wide field fluorescein angiography. This peripheral ischemic retina is likely a major VEGF production site. By selectively eliminating these ischemic areas with angiography-guided laser ablation while preserving more perfused areas of peripheral retinal, pathological levels of VEGF may be significantly reduced, translating into fewer necessary monthly intravitreal injections while preserving useful peripheral visual field. The study will include 3 cohorts followed for a total of 104 weeks.

Subjects will be randomized into one of three treatment cohorts in a 1:2:2 ratio.

Day 1 through Week 48:

- Cohort A (n=8) will receive monthly treatment of 0.5 mg ranibizumab for 48 weeks. Monthly treatment is defined as every 28 days (+/- 7 days).
- Cohort B (n=16) will receive monthly treatment of 0.5mg ranibizumab for 48 weeks. 1 week (+/-3 days) after the initial dose of ranibizumab is delivered, the subject will have peripheral targeted-retinal photocoagulation (TRP) to areas of peripheral retinal ischemia based on wide field angiography that was performed at the screen visit. After the first session of TRP, subjects will have a repeat wide field angiogram at week 24 and week 36 and will receive additional TRP as needed (PRN) to areas of peripheral retinal ischemia.
- Cohort C (n=16) will receive a loading dose (3 consecutive monthly doses) of 0.5mg ranibizumab followed by PRN treatment with 0.5mg ranibizumab. 1 week (+/- 3 days) after the initial dose of ranibizumab is delivered, the subject will have peripheral TRP to areas of peripheral retinal ischemia based on wide field angiography that was performed at the screen visit. After the first session of TRP, subjects will have a repeat wide field angiogram at week 24 and week 36 and will receive additional TRP as needed to areas of peripheral retinal ischemia.

See RRR protocol for TRP and PRN treatment criteria.

Week 52 through Week 101:

All cohorts will enter a treat and extend protocol for IVT ranibizumab retreatment beginning at week 52. At any visit where a dry macula is achieved din the study eye, the visit interval between IVT ranibizumab treatments will be lengthened by 1 week. A dry macula is defined as the resolution of recurrent or persistent fluid based on SD-OCT, slit lamp examination, and/or indirect ophthalmoscopy.

After a subject has been extended beyond a monthly visit interval between IVT ranibizumab treatments, the visit interval will be reduced by 1 week, if the study eye develops recurrent disease activity. Recurrent disease activity is defined as recurrent or persistent fluid based on SD-OCT, slit lamp examination, and/or indirect ophthalmoscopy.

IVT ranibizumab treatment will be administered in the study eye at every visit, no earlier than 7 days before the target date and no longer than 7 days after the target date. The visit interval between IVT ranibizumab treatments is individualized based on each patient's response to treatment. The visit interval between IVT ranibizumab treatments will not exceed 12 weeks.

2.1 Sample Size Calculations

A priori power calculation was performed and revealed that a sample size of n=41 was needed to achieve 80% power using single factor ANOVA with a significance level (alpha) of 0.05. Based on this result, the final study size was 40. Patients randomized in a 1:2:2 ratio. Sample size estimation was performed using RStudio (Version 1.1.463, RStudio Inc., Boston, Massachusetts). Statistical analyses were performed using Prism (GraftPad Software, San Diego, CA) and the data analysis function in Microsoft Excel (Microsoft Inc., Redmond, WA).

The reason for the 1:2:2 randomization ratio was that the monthly group would have less variability in terms of treatment course because each patient would receive an injection each month without alterations or additional factors to their treatment regimen, allowing for detection of the group's trend with a smaller cohort size. On the other hand, the other two cohorts could have different treatment schedules and therefore would require more patients to capture the trend. The exception to this randomization was that patients whose central vision of 20/50 or better at screening exam were randomized into the three cohorts in a 1:1:1 ratio in order to minimize a disproportionate population of subjects with good vision in any one group and to minimize the chance of significant difference in baseline vision between groups. Randomization occurred on Day 0 in which a randomly selected envelope containing a cohort assignment was chosen for each patient.

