4. MATERIALS AND METHODS

4.1. SUBJECTS

4.1.1. Subject Selection

40 subjects from 4 sites in the United States will be enrolled. Subjects who have provided informed consent will be screened for eligibility before the initiation of any study procedures. Screening evaluations may be performed at any time within 0 – 14 days preceding Day 0. These subjects must have active radiation retinopathy.

The subjects will be randomized in a 1:2:2 ratio so that:

- 8 subjects will receive monotherapy with monthly treatments of 0.5 mg ranibizumab for 48 weeks. Beginning at week 52, all subjects will enter a treat and extend protocol for IVT ranibizumab retreatment. (Cohort A)
- 16 subjects will receive combined therapy with monthly treatments of 0.5 mg ranibizumab and up to 3 sessions of targeted-retinal photocoagulation for 48 weeks. Beginning at week 52, all subjects will enter a treat and extend protocol for IVT ranibizumab retreatment. (Cohort B)
- 16 subjects will receive combined therapy with a loading dose (3 consecutive monthly doses) of 0.5 mg ranibizumab followed by PRN treatment of 0.5 mg ranibizumab and up to 3 sessions of targeted-retinal photocoagulation for 48 weeks. Beginning at week 52, all subjects will enter a treat and extend protocol for IVT ranibizumab retreatment. (Cohort C)

Any patients entering into the study with central vision of 20/50 or better on screening examination will be randomized 1:1:1 into the 3 treatment groups in order to minimize the chance of an accidentally skewed population of patients with good vision in one treatment group. There is no requirement that the study enroll any specific number of patients with good vision.

*See Appendix A, the study flow chart, for screening assessments.

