4.2. METHOD OF TREATMENT ASSIGNMENT

Upon eligibility confirmation, subject randomization will occur at Day 0 prior to receiving treatment by randomly selecting an envelope containing cohort assignment. Randomization envelopes will be divided into two categories: one for subjects with vision measuring 20/50 or better, and one for subjects with vision

measuring worse than 20/50. Subjects with vision measuring 20/50 or better will be randomized in a 1:1:1 fashion in order to minimize the chance of an accidentally skewed population of patients with good vision in one treatment group. Subjects with vision measuring worse than 20/50 will be randomized in a 1:2:2 fashion. Subjects will be randomized into 1 of the following 3 cohorts:

- **Cohort A:** Subjects receive monthly treatment of 0.5 mg IVT ranibizumab for 48 weeks. Beginning at week 52, all subjects will enter a treat and extend protocol for IVT ranibizumab retreatment.
- **Cohort B:** Subjects receive monthly treatment of 0.5 mg IVT ranibizumab for 48 weeks. 1 week (\pm 3 days) after the initial dose of IVT ranibizumab is delivered, the subject will have peripheral targeted-retinal photocoagulation (TRP) to areas of peripheral retinal ischemia based on 120° or greater wide field angiography that was performed at the screen visit. After the first session of TRP, subjects will have a repeat wide field angiogram at Week 24 and Week 36 and will receive additional TRP as needed (PRN) to areas of peripheral retinal ischemia. Beginning at week 52, all subjects will enter a treat and extend protocol for IVT ranibizumab retreatment.
- **Cohort C:** Subjects will receive a loading dose (3 consecutive monthly doses) of 0.5 mg IVT ranibizumab followed by PRN treatment with 0.5 mg IVT ranibizumab. 1 week (\pm 3 days) after the initial dose of IVT ranibizumab is delivered, the subject will have peripheral targeted-retinal photocoagulation (TRP) to areas of peripheral retinal ischemia based on wide field angiography that was performed at the screen visit. After the first session of TRP, subjects will have a repeat wide field angiogram at Week 24 and Week 36 and will receive additional TRP as needed (PRN) to areas of peripheral retinal ischemia. Beginning at week 52, all subjects will enter a treat and extend protocol for IVT ranibizumab retreatment.

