6. ANALYSES

All outcomes will be presented using descriptive statistics. For comparison of groups for primary and secondary outcomes, variables of interest will be statistically analyzed using analysis of variance (ANOVA), Student's t-tests, Chi square and Fisher's exact test. ETDRS data will be obtained for all visits

for all 40 of the participants. Bonferroni correction was applied to all pairwise comparison analyses for this study.

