6.1 Primary Outcome

The primary analysis will compare cohorts (A vs. B vs. C) on their mean change in ETDRS BCVA from baseline to week 48 and week 104 with the above described statistical tests. Adverse events will be reported using counts and percentages for each cohort.

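### The mixed 1:1:1 / 1:2:2 randomisation gives Cohort A a higher expected share of good-vision eyes, and the unadjusted primary comparison does not correct for it

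*SAP*

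**What the plan says.** **Allocation.** Protocol 4.1.1, Protocol 4.2 and SAP 2.1 describe two sets of envelopes. In SAP 2.1, "patients whose central vision of 20/50 or better at screening exam were randomized into the three cohorts in a 1:1:1 ratio". In Protocol 4.2, "Subjects with vision measuring worse than 20/50 will be randomized in a 1:2:2 fashion". Assignment is made "by randomly selecting an envelope containing cohort assignment"; block size, or whether blocks are used at all, is not stated. Protocol 3.2, Protocol 4.1.1 and SAP 2 give cohort sizes of 8, 16 and 16. Protocol 4.1.1 adds: "There is no requirement that the study enroll any specific number of patients with good vision".

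**Stated purpose.** One of the reasons SAP 2.1 gives for the 1:1:1 exception is "to minimize the chance of significant difference in baseline vision between groups".

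**Analysis.** SAP 6.1 will "compare cohorts (A vs. B vs. C) on their mean change in ETDRS BCVA from baseline to week 48 and week 104". The methods are those of SAP 6: "variables of interest will be statistically analyzed using analysis of variance (ANOVA), Student's t-tests, Chi square and Fisher's exact test". SAP 2.1 bases the sample size on a single-factor ANOVA. Neither document names the acuity stratum or baseline acuity as a factor, covariate or weight. Bonferroni correction is applied to pairwise comparisons.

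**The concern.** Equal expected numbers of good-vision eyes in cohorts of unequal size do not give equal proportions. The smallest cohort gets the highest share, which works against the balance that SAP 2.1 gives as the reason for the rule.

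Once the probability of assignment depends on acuity stratum, a crude comparison of cohort means mixes the treatment difference with the stratum difference. Analysing change from Day 0 does not remove this if the change itself depends on starting acuity. Bonferroni correction deals with multiplicity only.

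The trial sets out to assess targeted photocoagulation (Protocol 3.2, SAP 2). Cohort A is the only cohort without laser, and A versus B isolates laser on a monthly-injection background. The exposed contrasts are therefore the ones that answer the main question.

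**Working it through.** **Inputs from the documents.** N = 40; A:B:C is 1:1:1 at 20/50 or better and 1:2:2 otherwise; stated sizes are 8/16/16.

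**Assumptions, not in the documents.** The number of good-vision subjects G, the difference in mean change between strata D (5, 10 or 15 letters), the SD of change, and whether envelopes are blocked.

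**1. The stated sizes.** With W = 40 − G:

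- E[nA] = G/3 + W/5
- E[nB] = E[nC] = G/3 + 2W/5

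G = 0 gives 40/5 = 8 and 2 × 40/5 = 16, so 8/16/16 is the expected split only if no good-vision subject enrols. It can still occur by chance: in 39% of 3,000 simulated blocked allocations with G = 3, and in 20% with G = 6.

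**2. Expected good-vision share.** This is (G/3)/E[n] in each cohort.

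| G | E[nA] | E[nB] = E[nC] | Share in A | Share in B or C | Gap |
|---|---|---|---|---|---|
| 6 | 8.8 | 15.6 | 0.227 | 0.128 | 0.099 |
| 12 | 9.6 | 15.2 | 0.417 | 0.263 | 0.154 |
| 16 | 10.1 | 14.9 | 0.526 | 0.357 | 0.169 |
| 20 | 10.7 | 14.7 | 0.625 | 0.455 | 0.170 |

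The gap is positive for every mix of the two strata and peaks at 0.172 near G = 18.4. If totals were instead held at 8/16/16, A's share would be exactly twice that of B or C; for G = 12, 4/8 = 50% against 4/16 = 25%. B and C have the same chance in each stratum, so their expected shares are equal.

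**3. Bias in a crude A contrast.** Bias = gap × D.

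| G | D = 5 | D = 15 |
|---|---|---|
| 6 | 0.099 × 5 = 0.5 | 0.099 × 15 = 1.5 |
| 12 | 0.154 × 5 = 0.77 | 0.1535 × 15 = 2.30 |
| 16 | 0.169 × 5 = 0.85 | 0.1692 × 15 = 2.54 |

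**4. Against the standard error.** With an assumed SD of 15 letters, SE(A − B) = 15 × √(1/nA + 1/nB).

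- G = 12: 15 × √(1/9.6 + 1/15.2) = 6.18
- G = 16: 15 × √(1/10.13 + 1/14.93) = 6.10

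The bias therefore runs from 0.77/6.18 = 0.12 SE to 2.54/6.10 = 0.42 SE.

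**5. Simulation.** No treatment effect, SD 15, 5,000 runs per cell (Monte Carlo SE of the bias about 0.09 letters), G = 12 and 16, D = 10. A negative sign means good-vision eyes were assumed to gain less.

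| Quantity | Result |
|---|---|
| Crude A − B | −1.5 to −1.7 letters |
| Crude B − C | within 0.2 of zero |
| A − B adjusted for stratum | within 0.2 of zero |
| Crude A − B, 1:2:2 in both strata | 0.0 |

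A second simulation (unblocked, SD 12, 8,000 runs per cell, G = 12 and 20) gave crude A − B of −0.85 to −0.94 at D = 5, −1.52 to −1.79 at D = 10 and −2.32 to −2.56 at D = 15. The stratum-adjusted values were all within 0.06 of zero.

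**6. Size of the test.** Over D = 5 to 15 with SD 15 and nominal 0.05, the crude ANOVA rejected in 0.037–0.049 of runs with permuted blocks and 0.051–0.071 without. The stratum-adjusted model gave 0.049–0.055 either way. The case here rests on bias in the estimate, not on false positives.

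**The case against.** **The bias is conditional.** Only the share gap follows from the documents. It becomes bias only if mean change differs between strata, and no figure for that is given. This is right, and the letters above are a range under stated assumptions. The bias is zero if no good-vision subject enrols or if change does not depend on stratum.

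**The effect is small.** At 0.12 to 0.42 SE, with about ten subjects in Cohort A in a 40-subject phase II trial, imprecision outweighs bias. This also stands, and it limits the weight of the point. But the bias comes from the allocation rule itself, and removing it needs no new data.

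**SAP 2.1 speaks of the chance of a significant baseline difference, not of expected shares.** This is the strongest argument. A simulation with assumed baseline letters (uniform 65–80 for good vision, 20–64 for worse) found a significant baseline ANOVA in about 5–6% of trials under unstratified 1:2:2, and in 0.2–0.4% under the two-envelope scheme with permuted blocks. So a blocked version does reduce that chance. The gain comes from stratifying, however, and not from the 1:1:1 ratio. A blocked 1:2:2 ratio in both strata gave no more significant baseline differences, and a root-mean-square share gap of 0.00–0.06 against 0.10–0.18. Without blocking, which the documents do not mention, the two-envelope scheme produced a significant difference in about 10% of trials. The claim as written credits the mixed ratio with something it does not deliver.

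**The shift in cohort sizes is minor.** Expected sizes move by only one or two subjects, and Protocol 4.1.1 states the exception just below the sizes. That is fair; it is a wording correction.

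**Conclusion.** The concern holds. That Cohort A has a higher expected share of good-vision eyes is exact arithmetic from the two ratios, and no adjustment is written in either document. The gap is 10 points with 6 good-vision subjects of 40 and at most 17 points.

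The resulting bias in A versus B and A versus C depends on an unknown stratum difference in mean change. At an assumed 5 to 15 letters it is 0.5–1.5 letters with 6 good-vision subjects and about 0.8–2.5 letters with 12 or 16. The overall three-cohort test is affected too; B versus C is not. This is a modest, systematic error in the contrasts with the only non-laser cohort. It should be fixed, but it does not by itself undermine the trial.

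**What to change.** **SAP 6.1.** Replace the crude comparison with, for example:

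> BCVA change from Day 0 at week 48 and at week 104 will be compared between cohorts with a linear model including cohort, randomisation stratum (20/50 or better versus worse at screening, as used to choose the envelope) and baseline ETDRS letters. The A–B, A–C and B–C contrasts will be taken from this model with Bonferroni adjustment.

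The stratum term alone removes the bias. Baseline letters are preferable for precision but optional.

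**If the analysis has been done.** SAP 2.1 is partly in the past tense ("Statistical analyses were performed using Prism"). In that case keep the existing primary analysis and report the model above as a labelled sensitivity analysis.

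**SAP 2.1.** Remove the statement that the mixed ratio minimises baseline vision differences between groups.

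**SAP 2.1 and Protocol 4.1.1 and 4.2.** State that expected cohort sizes move away from 8/16/16 as subjects at 20/50 or better enrol (about 10/15/15 with 16 of 40), and say whether the envelopes are blocked. If randomisation is still open, use one ratio in both strata.

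**Cost.** No new patients or data, since stratum and baseline letters are already recorded at screening and Day 0. With 40 subjects the error degrees of freedom fall from 40 − 3 = 37 to 36 with stratum, and to 35 with baseline letters as well.
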